The purpose of this study is to determine the rate of occlusion in BioFlo implanted port-catheters flushed with 20 mL of normal saline only vs those flushed with the standard practice of 20 mL of normal saline followed by 5 mL of heparinized saline (100 units per mL). The researchers also hope to conclude that the complication rate in patients whose ports are flushed with saline only is no greater than those of patients whose ports are flushed with the combination of saline and heparinized saline. These complications might include partial or complete obstruction, infection of the central line, and/or the onset of heparin induced thrombocytopenia.

Research Question(s):

1. Does a saline only flush maintain the patency of BioFlo Port at a rate comparable to a heparinized saline solution?
2. Is there any difference in the type and rate of complications among BioFlo Ports flushed with saline only versus heparinized saline?

Null Hypothesis:

We are proposing a non-inferiority trial. Thus, the null hypothesis is: BioFlo Ports flushed with saline only will experience an occlusion rate of more than 10% over the occlusion rate experienced in implanted port catheters flushed with a heparinized saline solution.

The alternative hypothesis is: BioFlo Ports flushed with saline only will experience an occlusion rate less than 10% over the occlusion rate experienced in implanted port catheters flushed with heparinized saline solution.

Background Information/Literature Review:

Currently at TriHealth, Inc. all implanted port catheters are flushed according to the TriHealth Nursing Policy and Procedure Intravenous Site Guidelines (See Appendix A). An implanted port catheter is flushed with 20 mL of normal saline after IV medication, blood, or blood draws. Heparinized saline in the amount of 5 mL (concentration 100 units/mL) is used as a final flush

when no IV fluids are running and before de-accessing. This is intended to maintain patency of the catheter until the next use.

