During FY 2012, 391 patients with implanted port catheters were treated in the OPCC. Seventy of these patients experienced an occlusion of their port that required the administration of alteplase (CathFlo) ([name], personal communication, October 12, 2012). Thus, 70 of 391 experienced an occlusion resulting in an occlusion rate of 18%. Some of these 70 patients experienced an occlusion more than once during that time. Additionally, during that time, a few patients had their implanted port catheters removed due to infection or malfunction. The exact number of patients who experienced multiple occlusions or had their implanted ports removed/replaced during FY2012 is unknown.

During the planning of the current study evaluating implanted port catheters, we engaged the consultation of a biostatistician through the Center for Clinical and Translational Science and Training (CCTST) to conduct a power analysis to

establish the number of participants needed in each group to determine the non-inferiority of the alternative therapy (saline only flush). Consultation was provided by [name], Associate [name] Hospital Medical Center, University of Cincinnati.

Based on the literature and our own experience we estimated an approximate occlusion rate of 20% with the standard treatment (saline + heparinized saline flush as described above). The power analysis conducted by [name] determined that, using a two group normal approximation test of proportions with a one-sided .05 significance level, a sample size of 198 participants per group will have 80% power to reject the null hypothesis that the proposed method is not inferior (i.e. the difference in proportions between the proposed method and the standard method is greater than 0.10). Thus, we will continue to recruit participants in that study until 198 have been enrolled in each group for a total of 396 study participants.

[name] was consulted again when the introduction of the BioFlo Port at TriHealth was discovered. It is [name] recommendation that this second randomized controlled trial using the same methodology and power analysis calculations be conducted. Thus, we will recruit 198 participants per group for a total of 396 participants in this study.

Data Collection:

Independent Variables: Method for flushing implanted port catheters:

- 20 mL of saline followed by 5 mL of Heparinized saline in a concentration of 100 units/mL
OR
- 20 mL of saline only

Dependent Variables:

Primary Outcomes

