The data collection tool (see Implanted Port Catheter Flushing Data Collection Form – Face Sheet: Appendix C and Record of Flushes: Appendix D) were developed by the principal and sub-investigators specifically for the purpose of this study. The tool was reviewed by the OPCC nurses for completeness and clarity. In addition to basic demographic information (age, gender), the nurse will record the patient's type of cancer, and the diagnosis or history of any hypercoaguable state or use of anticoagulant medication as documented in the patient chart. The nurse will also document the type of implanted port catheter (single/double), the port location (right/left, subclavian vein (described in the operative note or chest x-ray), and the date the port was inserted so that length of time the port has been in place can be calculated. Data will be recorded on the Face Sheet when the patient is enrolled in the study and as pertinent information/events become known, i.e., as complications occur.

With each visit to the identified treatment center, the nurse will document the date and characteristics related to the patency of the port catheter on

the Record of Flushes data collection tool. In the event the blood withdrawal is sluggish or absent, the patient will receive a dose of alteplase (CathFlo) according to the TriHealth Nursing Policy: VAD: Care & Maintenance (Appendix A) and as ordered by the physician. Dosage and results of that intervention will also be recorded on the Record of Flushes data collection tool. In the event that any study participant (regardless of group assignment) requires alteplase (CathFlo) on three (3) consecutive visits to the treatment center, the patient's participation in the study will be terminated and they will be excluded from further data collection. The patient will be returned to a standard maintenance protocol for flushing of the port as prescribed by the afore-mentioned TriHealth Nursing policy (see Appendix A) or as prescribed by attending physician.

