Potential risks for study participants in either arm of the study include partial occlusion (can instill flush solution but not withdraw blood) and complete occlusion (can neither instill flush solution nor withdraw blood). Study participants could require removal of the port if an occlusion cannot be resolved, and possibly require re-insertion of a new implanted port. In the event of any occlusion, alteplase (CathFlo) in the policy established dose and frequency (see Appendix A) will be instilled to resolve the occlusion. Study participants whose implanted ports are found occluded on three (3) consecutive visits to the treatment center will be excluded from further data collection, i.e., their participation in the study will be terminated. The standard flushing as prescribed by the TriHealth Nursing Policy (see Appendix A) or as prescribed by the attending physician will be used. Study participants whose occlusion cannot be resolved with alteplase and require removal of the port will also be terminated and excluded from further data collection. Patients who develop port infections necessitating port removal will be terminated and excluded from further data collection. Study participants who develop HIT (heparin induced thrombocytopenia) or other heparin allergy will be terminated and excluded from further data collection. Likewise, patients who have thrombotic or embolic phenomenon requiring therapeutic anticoagulation will be terminated and excluded from further data collection.

The study will be closed if there is evidence that study participants in the intervention arm experience implanted port occlusion at a disproportionate rate. The amount of alteplase (CathFlo) used in each group will be assessed each month for monitoring purposes.

The undertaking of this research does require the participation of other personnel, facilities or departments other than those used in data collection. In the event the study participant is admitted to the hospital or requires some intervention using their implanted port catheter (e.g., CT scan with contrast), the study participant will have an information card describing his/her participation in the study and the group to which he/she has been randomized, so that the assigned flush solution is used, and integrity of the study can be maintained. The study participant will receive the card with instructions at the time of his/her enrollment in the study (see Appendix E Wallet Study Card).

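### The protocol body describes no record of the flush solution used when the port is accessed outside the study centers, where the institutional default is heparin

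*Combined protocol and SAP*

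**What the plan says.** - **Default flush.** Background Information/Literature Review: "Currently at TriHealth, Inc. all implanted port catheters are flushed according to the TriHealth Nursing Policy and Procedure". Under that policy the last flush before the needle is removed is 5 mL of heparinized saline, which is also the control regimen.
- **Use elsewhere.** Experimental Aspect of the Study accepts that other departments will handle the port, naming hospital admission and contrast CT. The stated measure is a card that the participant carries, showing the assigned group, "so that the assigned flush solution is used, and integrity of the study can be maintained".
- **Training and flags.** Privacy Information limits study training to treatment-center nurses. The colored sticker and Face Sheet stay with the treatment-center folder.
- **Recording.** Data collection tool: "With each visit to the identified treatment center, the nurse will document the date and characteristics related to the patency". Alteplase dose and result go on the same form. The Face Sheet is updated as complications come to light.
- **Analysis.** Statistical Analysis lists t-test, Chi-Square or Fisher's exact test, a regression on the moderating variables, and strata by flush frequency. It names no analysis set and no summary of adherence to the assigned flush.

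**The concern.** A department that follows house policy gives a control participant the assigned flush and a saline participant the wrong one. Default-driven errors therefore move people mainly from saline to heparin. If heparin lowers the occlusion rate, those errors pull the saline arm toward the control arm. In a superiority trial that would be conservative. In a non-inferiority trial it favours the claim the sponsor hopes to make, and the result is meant to inform flushing policy.

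The sample size assumes that everyone receives the assigned solution. If the solution used elsewhere is not recorded, the report cannot show how often the card worked. Two other variables are also exposed: occlusions found elsewhere may reach the data only if someone happens to report them, and flush frequency, which is both a moderating variable and the stratification factor, may be undercounted.

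**Working it through.** **Inputs** (Recruitment section, sample-size paragraphs)
- Test: "using a two group normal approximation test of proportions with a one-sided .05 significance level".
- Size and power: "a sample size of 198 participants per group will have 80% power".
- Control rate: "we estimated an approximate occlusion rate of 20% with the standard treatment". Equal true rates are implied, not stated.
- Margin: "the difference in proportions between the proposed method and the standard method is greater than 0.10".
- Recruitment: "we will recruit 198 participants per group for a total of 396 participants in this study", with no addition for crossover.
- Share of the effect lost to crossover: not in the documents. It is assumed below and shown as a range.

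**Step 1: reproduce the plan's figure.** With pT = pC = 0.20:

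n = (1.645 + 0.842)² × (0.16 + 0.16) / 0.10² = 197.8, rounded up to 198 per group.

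The stated size is correct on its own inputs.

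**Step 2: effect of dilution.** Place the truth at the margin, 30% on saline and 20% on heparin, so that a non-inferiority claim is an error. If crossover removes a share c of the difference, the saline arm's rate becomes pT = 0.20 + 0.10 × (1 − c). Then

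SE = √[0.20 × 0.80/198 + pT(1 − pT)/198]

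P(claim) = Φ[(0.10 − (pT − 0.20))/SE − 1.645]

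| Share lost, c | pT | SE | P(false claim) |
|---|---|---|---|
| 0 | 0.300 | 0.0432 | 5.0% |
| 1% | 0.299 | 0.0432 | 5.2% |
| 3% | 0.297 | 0.0432 | 5.8% |
| 10% | 0.290 | 0.0430 | 7.9% |
| 20% | 0.280 | 0.0427 | 12.0% |

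Exact binomial enumeration, run at 0, 10% and 20%, agrees within 0.1 point.

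The quantity c is the share of the *effect* lost, not the share of patients who cross over. If the effect scales with the number of flushes, a 10% loss needs roughly 10% of all saline-arm final flushes to have been heparin.

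**Step 3: check the obvious remedy.** One might stop counting a saline participant at the first heparin flush and compare crude proportions. Off-site default heparin is the control assignment, so this removes follow-up almost only from the saline arm. Assume 30% versus 20% at 12 months, a constant hazard, and censoring at six months. The six-month saline risk is 1 − √0.70 = 0.163.
- 10% censored: pT = 0.9 × 0.30 + 0.1 × 0.163 = 0.286, and P(false claim) is about 9%.
- 20% censored: pT = 0.8 × 0.30 + 0.2 × 0.163 = 0.273, and P(false claim) is about 16%.

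A crude per-protocol comparison can therefore add bias in the same direction.

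**Step 4: cost of requiring two analyses to agree.** Power is 80% with 198 per arm and equal rates of 20%. Removing 10% or 20% of the saline arm (178 or 158 left) gives about 78% or 76% by the same formula. Requiring agreement would make the per-protocol analysis co-primary in a design with no power to spare.

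**The case against.** The strongest reply is that the gap may be small or already covered.

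- The Face Sheet, Record of Flushes and wallet card are Appendices C, D and E, and their content was not available. The form may ask for the solution, or the card may ask staff to report back. A reader might infer that the trial collects nothing that could reveal crossover. The documents do not support that; they support only that the protocol body describes no such record.
- The Face Sheet takes complications as they become known, so an occlusion found elsewhere may be captured. The enrollment log links study codes to medical record numbers for checking missing data, and consent is documented in the electronic health record. These are possible routes to detection, but none is presented as a check on the solution used.
- Eligibility requires routine port care at the study centers and expected care there for 12 months. Use elsewhere should be the exception, and the assigned flush resumes at the next visit.
- If the two solutions are equivalent, crossover produces no false conclusion.
- The heparin default is documented only for this institution.

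All of this stands and limits the likely size. It does not supply the missing record: the protocol expects the event and relies on the card, but describes no way to tell whether the card worked.

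**Conclusion.** The concern holds as a gap in what the protocol body describes. Off-site use is expected, the default there is the control flush, the only stated safeguard is a card carried by the patient, and no capture of the solution used is described. Any resulting crossover would run mainly from saline to heparin and, if heparin protects, would favour non-inferiority.

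Its size cannot be read from the documents. The error moves from 5.0% to between 5.2% and 5.8% if 1% to 3% of the effect is lost, and to 7.9% or 12.0% if 10% or 20% is lost. These figures assume a true difference exactly at the margin and a 20% control rate. Since routine care is at the study centers, the lower end is more plausible, but that is a judgement.

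A reader might conclude that a favourable result could not be defended at all. The documents do not support that: they give no off-site flush frequency and no evidence that a large share of saline-arm flushes would be heparin. The reason to act is that the frequency is unknown and cheap to measure.

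**What to change.** - **Record.** Unless Appendix D already does so, add a line to the Record of Flushes, completed at each center visit and checked against the electronic health record: whether the port was accessed elsewhere since the last visit, the solution used, and any occlusion or alteplase.
- **Count.** Include those occlusions in the primary outcome and those flushes in flush frequency.
- **Analyse.** State that the as-randomised comparison is primary, and report crossover by arm. Add a per-protocol analysis that is supportive, not co-primary, using a method that accounts for unequal follow-up, such as time to first occlusion. State that censoring at crossover may be informative, because participants who are admitted may differ in occlusion risk.

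The cost is a little nurse time at each visit, a short chart check and one extra analysis. The sample size and flush regimens are unchanged.

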provided. The BioFlo Port with PASV Valve Technology also claims to provide fewer complications when compared with nonvalved ports, namely a 47% ($p=0.02$) reduction in inadequate blood draw, a 51% ($p<0.03$) reduction in nursing time for troubleshooting port problems, and a 35% ($p=0.20$) reduction in tPA usage (Carlo, Lamont, McCarty, Livingston, & Kuhn, 2004). In the study by Carlo et al., the valved ports were flushed with 10 mL of normal saline while the nonvalved ports were flushed with 10 mL of heparinized saline (number of units of heparin per mL of saline not specified). These results are promising but it only included 73 patients (37 in valved port group and 36 in the non-valved port group) who were followed for 180 days. Additionally, it is only one study; subsequent studies replicating this methodology have not been located. The purpose of the MicroCLAVE® Clear connector which is used with all implanted port catheters at TriHealth is to also help minimize blood reflux into the tip of the catheter upon connection and disconnection of the luerloc, thus reducing the risk of occlusions due to blood reflux. Therefore, in this study and the one already in progress, the type of flushing solution is the main focus as the materials and mechanics of the implanted port in each study are the same.

In conclusion, Level 1 evidence for the use heparin flushes versus saline flushes for the maintenance of implanted port catheters is lacking in the current literature. No study has been conducted exclusively among patients with implanted port catheters of the same type. For nursing to establish an evidence-based practice guideline for flushing of implanted port catheters, more research is needed to generate the knowledge necessary to make recommendations that will change and standardize practice.

Research Plan

Study Design: Non-inferiority trial in which participants will be randomly assigned to one of two groups: the control group or the intervention group.

Setting for the Study: The TCI Infusion Centers, specifically: the TCI Good Samaritan (GS) Infusion Center at GSH; the TCI GS Infusion Center Butler County; the Ambulatory Treatment Center at Bethesda North Hospital; the TCI GS Infusion Center, Cheviot; TCI Infusion Center, Kenwood; TCI Infusion Center, Arrow Springs; and the TCI GS Infusion Center, Anderson.

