- Occurrence of first complete (can neither withdraw blood nor flush the catheter) occlusion
- Occurrence of first partial (able to flush but unable to withdraw blood) occlusion
- Frequency with which alteplase (CathFlo) has to be utilized to resolve an occlusion

Secondary Outcomes

- Number of subsequent occurrences of complete or partial occlusions after the first occurrence.
- Amount of time in days that a port remains patent (flushes easily and able to obtain a blood return).
 - Amount of time between entrance in study and first incidence of partial or complete occlusion

- Amount of time between incidences of partial or complete occlusion.
- Occurrence of other complications:
 - Central Line-Associated Blood Stream Infection (CLABSI) – a laboratory-confirmed (recognized pathogen cultured from one or more blood cultures; organism cultured from blood is not related to an infection at another site) blood stream infection that is considered central line associated (CDC, 2012).
 - Develops complication related to Heparin
 - HIT (Heparin induced thrombocytopenia as measured by a positive HIT antibody test)
 - Other heparin allergy

Moderating variables: other things that could also affect patency of the port

- Number of times port flushed per month or frequency of flushing.
- Use of prophylactic doses of anticoagulant drugs (e.g., enoxaparin, heparin, warfarin)
- Development of a hypercoaguable state, as diagnosed by primary hematologist/oncologist
- Mechanical difficulties related to port placement e.g. “Pinch-off syndrome”
- Length of time port has been in place prior to entrance in study

Extraneous variables:

- Type of cancer
- Age of participant

Data collection tool

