Statistical Analysis: Descriptive statistics will be used to describe the participants. Differences between groups on the dependent variables will be calculated using t-test, Chi-Square or Fisher's exact test as appropriate for the level of data under analysis (also see discussion regarding interim analysis). Regression analysis will be used to determine the effect of the moderating variables on the occurrence of occlusion in the implanted ports. Participants in the

control group and intervention group will be further stratified based on frequency of port flushing. Differences in the rate of occlusion between stratified groups will also be calculated.

Ethical Considerations: The purpose of this study is to determine the safest and most effective flushing solution(s) for maintaining patency in implanted port catheters. In so doing, study participants could be placed at potential risk for catheter occlusion. All catheter occlusion will be treated according to TriHealth policy, i.e., the instillation of alteplase (CathFlo) (see Appendix A). Potential study participants will be made aware of the risk when enrolled in the study (See Appendix B) script for recruiting patients into the study and the Informed Consent Statement).

Informed Consent: Patients who meet inclusion criteria will be approached by a member of the research team who will explain the study, implications of their participation and review the Informed Consent Statement and HIPAA Authorization Forms (see the attached). One signed copy of the Informed Consent Form and HIPAA forms will be given to the study participant and another placed in their folder in the TriHealth Infusion Center to be scanned into their EPIC electronic health record (EHR). The original signed Informed Consent Statement and HIPAA will be stored in a locked drawer in a TriHealth office until the study is completed and closed with the IRB. The RN seeking consent and PI will document the informed consent process in the participant's EHR. Additionally, the blue or yellow sticker on the patient folder in the treatment center and presence of data collection forms in the patient folder will indicate that the patient is a participant in the study.

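### The analysis section plans only tests of a zero difference for the primary occlusion comparison and never states the non-inferiority test for which the trial was designed and sized

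*Combined protocol and SAP*

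**What the plan says.** The design is stated three times, consistently:

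- **Null Hypothesis:** the null is that "BioFlo Ports flushed with saline only will experience an occlusion rate of more than 10% over the occlusion rate" seen with heparinized saline. The alternative is an excess below 10%.
- **Research Plan, Study Design:** "Non-inferiority trial in which participants will be randomly assigned to one of two groups".
- **Recruitment, power analysis paragraph:** the sample size was found "using a two group normal approximation test of proportions with a one-sided .05 significance level", with 80% power, 198 per group and an assumed control occlusion rate of 20%. The hypothesis to be rejected is that "the difference in proportions between the proposed method and the standard method is greater than 0.10".

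The Statistical Analysis section then covers every dependent variable with one sentence: "Differences between groups on the dependent variables will be calculated using t-test, Chi-Square" or Fisher's exact test, according to the type of data. It adds regression on the moderating variables and comparisons within flushing-frequency strata. It does not mention the margin, the one-sided level, a confidence interval or the power analysis. It points to a discussion of interim analysis, and the text supplied contains none.

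The Primary Outcomes list has three entries: first complete occlusion, "Occurrence of first partial (able to flush but unable to withdraw blood) occlusion", and "Frequency with which alteplase (CathFlo) has to be utilized to resolve an occlusion". None is named as the outcome to which the 0.10 margin applies.

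**The concern.** A chi-square, Fisher or t-test in its usual form asks whether the two groups differ at all. The trial asks whether saline only is worse by less than 10 percentage points. Neither result of a zero-difference test answers that. A significant result can occur with an excess below the margin, and a non-significant one can occur with an excess above it.

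An analyst who follows the Statistical Analysis section would therefore not run the test the trial was sized for. The protocol does not say how a non-significant result would be read. The first research question asks whether patency is comparable, which invites the reading that no significant difference means comparable. The stated aim is to change flushing policy if appropriate, so a wrong conclusion would carry into practice.

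**Working it through.** **Inputs.** From the power analysis paragraph: control rate 0.20, margin 0.10, one-sided level 0.05, power 0.80, 198 per group. The observed FY 2012 rate is 70/391 = 18%. Assumptions, because the protocol gives no figure: equal true rates under the alternative, no dropout, and a 0.05 level for the difference tests.

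**1. Reproduce the sample size.** For a margin test with equal true rates,

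n = (z₀.₉₅ + z₀.₈₀)² × 2p(1−p) / margin² = (1.645 + 0.842)² × 2 × 0.20 × 0.80 / 0.10² = 197.84 with unrounded quantiles, so **198 per group**.

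The plan's figure is matched exactly. A difference test of 20% against 30% at the same power would need 231 per group (one-sided) or 294 (two-sided). With 198 per group, the chi-square test has power 0.634 (two-sided) or 0.746 (one-sided) for that difference. The stated 80% describes neither.

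**2. Compare the rules at a true 10-point excess.** All outcomes of two independent binomials with n = 198 were enumerated. The chi-square has no continuity correction. The margin rule is (difference + 1.645 × unpooled standard error) < 0.10. The chi-square columns give the chance of a non-significant result, which counts as accepting saline only if non-significance is read as comparable.

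| True rates, heparinized saline vs saline only | Chi-square, two-sided | Chi-square, one-sided | Margin rule |
|---|---|---|---|
| 20% vs 30% | 36.6% | 25.4% | 5.0% |
| 18% vs 28% | 33.9% | 23.2% | 5.0% |
| 10% vs 20% | 19.3% | 11.9% | 5.3% |
| 5% vs 15% | 7.3% | 3.8% | 5.7% |

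Two-sided Fisher's exact test is non-significant in 40.8%, 38.2%, 23.7% and 9.9% of trials in the same four rows. With both true rates at 20%, the margin rule succeeds 80.0% of the time, as planned.

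**3. Where the rules disagree.** Take 40/198 occlusions on heparinized saline. The margin rule is met with at most 46 on saline only (upper limit 0.098) and fails at 47 (0.104). The chi-square stays non-significant up to 53 (one-sided) or 56 (two-sided).

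**4. An example that holds at either sidedness: 40/198 vs 53/198.**

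- Difference = 13/198 = 0.0657.
- Pooled rate = 93/396 = 0.235. Chi-square p = 0.123 two-sided, 0.062 one-sided: not significant.
- Unpooled standard error = √(0.202 × 0.798/198 + 0.268 × 0.732/198) = 0.0425.
- One-sided 95% upper limit = 0.0657 + 1.645 × 0.0425 = 0.136, or 13.6 points, which is above 10. Non-inferiority is not shown.

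**The case against.** The strongest reply is that the rule is nearly there already. The hypotheses carry the margin, and the power analysis names a test of proportions, its level and the difference to be rejected. Under the stated null, a failure to reject means that non-inferiority has not been shown, and nowhere does the protocol say a non-significant chi-square counts as success. This has force. The error rates for the difference tests are a possible consequence, not the plan's own error rate. But the margin test appears only as an input to the sample size, while the section that governs the analysis assigns different tests to all dependent variables and does not refer back. The two places have to be reconciled on any reading.

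A second reply is that 18% to 20% may be too high for this device. The 18% is from FY 2012, apparently before the BioFlo Port was introduced at these sites, and the 20% was set for the earlier port study. This also stands in part. At 10% vs 20% the inflation is smaller. At 5% vs 15% the one-sided chi-square errs less often than the margin rule (3.8% against 5.7%). That limits the size of the harm but does not supply the missing test.

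Third, any replacement text has to name an outcome, and a combined first occlusion is not itself on the primary list. The 18% counted patients whose occlusion required alteplase, which may not be the same event. This is correct, and it is why the choice is left to the sponsor below.

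The listed tests are ordinary choices for the secondary outcomes and are not in dispute there.

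**Conclusion.** The concern holds and should be corrected before analysis. The sample size is right for the stated design. The fault is that the analysis section prescribes tests that do not address the primary hypothesis and gives no decision rule. This conclusion needs no assumption.

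The size of the consequence is conditional on a 0.05 level, 198 analysed per group and non-significance being read as comparable. On those terms the chance of wrongly accepting saline only at the margin is about 5 to 7 times the intended 5% at the planning rates (25.4/5.0 = 5.1 one-sided; 36.6/5.0 = 7.3 two-sided). It falls as occlusion rates fall and is largely gone by 5% vs 15%.

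**What to change.** For the primary comparison only, replace the difference test in Statistical Analysis with a rule such as:

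> Non-inferiority is concluded if the upper limit of the one-sided 95% confidence interval (the upper end of the two-sided 90% interval) for the difference in the proportion of participants with a first occlusion, partial or complete, during the 12-month study period, saline only minus heparinized saline, is below 0.10. A non-significant chi-square or Fisher test is not evidence of non-inferiority.

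The sponsor has two decisions to make:

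1. Confirm that combined first occlusion is the outcome the margin governs, or name another. The choice should be checked against the planning rate, which counted occlusions needing alteplase.
2. State how participants who leave before 12 months without an occlusion enter the proportion. Under Experimental Aspect of the Study, for example, "patients who have thrombotic or embolic phenomenon requiring therapeutic anticoagulation will be terminated and excluded from further data collection".

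Keep the listed tests for the secondary outcomes. Supply the interim-analysis discussion or delete the pointer to it. In the power analysis paragraph, reword the null as inferior by more than 0.10. It now describes the null as the method being not inferior, against its own parenthesis and the Null Hypothesis section.

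The cost is a few sentences and the two decisions. The sample size stays at 198 per group and no further data are needed. With this rule the enumeration gives 80.0% power at 20% in both groups and 5.0% error at 20% vs 30%, as the plan intends.
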